12.1.3. Electrocardiograms

Single 12-lead ECGs are to be performed for all subjects.

On Day 1, ECGs are to be performed up to 2 hours before and 4 hours (-1 hour/+ 2 hours) after the first study drug dose [REDACTED]

For calculated ECG parameters, the following web site should be used:

<https://www.mdcalc.com/corrected-qt-interval-qtci#next-steps>

12.1.4. Eye Examinations

Eye examinations are to be performed for all subjects by a qualified ophthalmologist or optometrist.

Near and far visual acuity is to be assessed by an ophthalmologist or optometrist using standard measures (e.g., Early Treatment Diabetic Retinopathy Study or similar) in each eye. If the subject wears corrective lenses (e.g., glasses), then visual acuity is to be checked first with corrective lenses and then without correction. A best-corrected examination is not required.

A slit lamp examination (biomicroscopy), including examination of the eyelids, conjunctiva, cornea, anterior chamber, iris, and lens, is to be performed after completion of visual acuity testing for the determination of corneal health.

Eye exams at Week 4, Week 8, Week 13, Week 26, Week 39, Week 52, Week 56 and/or Early Termination are required only if eye-related signs or symptoms are reported by the subject or observed by the investigator.

If a subject experiences a treatment-emergent eye abnormality, an ophthalmologic examination should be performed by a qualified ophthalmologist or optometrist within 24 to 48 hours or on the next business day after symptom onset to evaluate the abnormality.

12.1.5. Safety Laboratory Assessments

Blood and urine samples are to be collected for hematology, clinical chemistry, and urinalysis. The safety laboratory parameters to be measured are presented in [Table 5](#).

Table 5: Safety Laboratory Parameters

Hematology	
Hematocrit	Platelet count
Hemoglobin	White blood cell count with differential
Red blood cell count	Absolute neutrophil count
MCV	MCHC
Coagulation Studies	
Prothrombin time	Fibrinogen
INR	aPTT
Chemistry (Fasting)	
Chloride	Carbon dioxide
Sodium	Potassium
Blood urea nitrogen	Calcium
Creatinine	Magnesium
Albumin	Glucose
Total protein	Alkaline phosphatase
AST*	ALT*
GGT	eGFR (Screening only)
Total, indirect, and direct bilirubin	
Creatine phosphokinase (total and fractionated) (Screening and Baseline only)	
Urinalysis	
Specific gravity	Protein
pH	Ketones
Blood	Microscopic examination of sediment
Glucose	
Other	
Serum or urine β -hCG [†]	

*AST and ALT collected as part of the clinical chemistry panel are also applicable for efficacy assessments.

† Serum β -HCG pregnancy testing is to be performed for female subjects of childbearing potential during Screening, and a urine pregnancy test is to be performed within 24 hours before the first dose on Day 1 (Baseline). Subjects with a positive serum pregnancy test result are not eligible for study participation. Serum pregnancy testing is to be repeated at the Week 56 Follow-up visit or at Early Termination (whichever takes place sooner), and during the study any time pregnancy is suspected. Female subjects of childbearing potential are required to perform urine home pregnancy tests monthly between study visits and the results should be recorded in a subject diary. A positive urine test should be followed by an unscheduled serum pregnancy test as soon as possible. Study drug is to be held in the event of a positive urine pregnancy test and permanently discontinued for any subject with a positive serum pregnancy test result.

Abbreviations: β -HCG = beta human chorionic gonadotropin; ALT = alanine aminotransferase; aPTT = activated partial thromboplastin time; AST = aspartate aminotransferase; eGFR = estimated glomerular filtration rate; GGT = gamma-glutamyltransferase; INR = international normalized ratio; MCHC = mean corpuscular hemoglobin concentration; MCV = mean corpuscular volume.

Liver enzyme tests determined as part of the clinical chemistry panel will also be used for the assessment of efficacy endpoints.

Clinical laboratory evaluations are to be repeated as necessary during treatment at a schedule determined by the Investigator, based on the subject's clinical status.

Laboratory abnormalities that are considered by the Investigator to be clinically significant for a particular subject are to be reported as an AE.

Information regarding alcohol and urine drug screening is provided in Section [10.5](#).

12.1.6. Anthropometric Assessments

Anthropometric assessments are to be performed, including:

- Weight (without shoes or heavy clothing) (kg), with calculation of BMI using Screening height and weight.
- Waist circumference at umbilicus (cm)
- Hip circumference (cm)
- Waist-hip ratio

12.2. Adverse and Serious Adverse Events

12.2.1. Definition of Adverse Events

12.2.1.1. Adverse Event

An AE is any untoward medical occurrence in a subject or clinical investigation subject administered a pharmaceutical product, and which does not necessarily have to have a causal relationship with this treatment. An AE can therefore be any unfavorable and unintended sign (including abnormal laboratory findings), symptom, or disease temporally associated with the use of an investigational product, whether or not related to the investigational product.

AEs also include the following:

- Complications that occur as a result of a protocol-mandated procedure (e.g., venipuncture, biopsy).
- Any pre-existing condition that increases in severity, or changes in nature during the study or as a consequence of the study treatment.
- Complications and termination of pregnancy (see Section [12.2.6](#) for additional information).
- Any symptom (e.g., myalgia, fever), physical examination finding, or clinical syndrome (e.g., coryzal illness) that occurs as a result of infection and/or following COVID-19 vaccination and is believed by the Investigator to be linked to the viral infection or immunization. (Further details for EDC update are contained within the EDC completion guidelines.)

An unexpected AE is any event for which the nature or severity is not consistent with the information in the current Investigator's Brochure.

All AEs that occur from Screening (i.e., after the informed consent form [ICF] is signed) through 28 days after the last dose of study drug, whether or not they are related to the study drug, are to be reported in the eCRF.

12.2.1.2. Serious Adverse Event

An AE or suspected adverse reaction is considered serious if, in the view of either the Investigator or Sponsor, it:

- Results in death.
- Is life-threatening. Life-threatening means that the subject was at immediate risk of death from the reaction as it occurred, i.e., it does not include a reaction which hypothetically might have caused death had it occurred in a more severe form.
- Requires in-patient hospitalization or prolongation of existing hospitalization. Hospitalization admissions and/or surgical operations scheduled to occur during the study period, but planned prior to study entry are not considered AEs if the illness or disease existed before the subject was enrolled in the study, provided that it did not deteriorate in an unexpected manner during the study (e.g., surgery performed earlier than planned). Additional exclusions to SAE reporting include hospitalizations for:

Elective procedures that are planned at the time of signing the informed consent.

Social/administrative reasons in the absence of an AE.

Expected deterioration caused by progression of the underlying disease.

- Results in persistent or significant disability/incapacity. Disability is defined as a substantial disruption of a person's ability to conduct normal life functions.
- Is a congenital anomaly/birth defect.
- Is an important medical event. An important medical event is an event that may not result in death, be life-threatening, or require hospitalization but may be considered an SAE when, based upon appropriate medical judgment, it may jeopardize the subject and may require medical or surgical intervention to prevent one of the outcomes listed in the definitions for SAEs. Examples of such medical events include allergic bronchospasm requiring intensive treatment in an emergency room or at home, blood dyscrasias or convulsions that do not result in in-patient hospitalization, or the development of drug dependency or drug abuse.

All SAEs that occur after any subject has been enrolled, before treatment, during treatment, or within 28 days following the cessation of treatment, whether or not they are related to the study drug, must be recorded on EDC or paper forms (if applicable) provided by Sagimet Biosciences, or designee.

12.2.2. Adverse Event Assessment

12.2.2.1. Intensity

The intensity of each AE is to be assessed by the Investigator according to the National Cancer Institute (NCI) Common Terminology Criteria for Adverse Events (CTCAE) (see https://ctep.cancer.gov/protocoldevelopment/electronic_applications/docs/CTCAE_v5_Quick_Reference_5x7.pdf). If the AE is not included in the NCI CTCAE, then the Investigator is to determine the intensity of the AE according to the following criteria:

Mild (Grade 1): AE that disappears or is easily tolerated on continuation of study drug.

Moderate (Grade 2): AE sufficiently discomforting to cause interference with usual work activities.

Severe (Grade 3): AE that is incapacitating, with inability to work or perform daily activities.

Life-Threatening (Grade 4): AE that is *potentially* life-threatening.¹

Death (Grade 5): Death related to AE.

12.2.2.2. Relationship to Study Drug

The causal relationship of each AE to study drug will be determined by the Investigator according to best medical judgment, as follows:

Definitely related: This category applies when, after careful medical consideration, there is almost no consideration of other causation.

Probably related: There is a clinically plausible time sequence between onset of the AE and study drug administration. The AE is unlikely to be caused by a concurrent and/or underlying illness, other drugs, or procedures. If applicable, the AE follows a clinically consistent resolution pattern upon withdrawal of study drug.

Possibly related: There is a clinically plausible time sequence between onset of the AE and study drug administration, but the AE could also have been caused by the concurrent and/or underlying illness, other drugs, or procedures. Information regarding study drug withdrawal may be lacking or unclear. “Possible” should be used when study drug administration is one of several biologically plausible causes of the AE.

¹. If a life-threatening (Grade 4) adverse event is *immediately* life-threatening, the event is, by definition, serious and is to be reported as described in Section 12.2.4.

Unlikely related: The AE is most likely due to a non-study drug-related cause. However, association with the study drug cannot be completely ruled out.

Unrelated: Another cause of the AE is most plausible, and a clinically plausible temporal sequence is inconsistent with the onset of the AE and study drug administration and/or a causal relationship is considered biologically implausible.

If the relationship between the AE/SAE and study drug is determined to be “possible”, “probable”, or “definite”, the event will be considered to be treatment-related for the purposes of expedited regulatory reporting and safety analyses.

12.2.2.3. Seriousness

AEs that meet the criteria specified in Section 12.2.1.2 are to be considered serious.

12.2.3. Recording Adverse Events

Each subject must be carefully monitored for the development of any AEs. This information should be obtained in the form of non-leading questions (e.g., “How are you feeling?”) and from signs and symptoms detected during each physical examination, observations on the part of study personnel, and spontaneous reports from subjects.

All AEs (serious and non-serious) spontaneously reported by the subject and/or in response to an open question from study personnel or revealed by observation, physical examination, or other diagnostic procedures will be documented in the subject’s source documents and recorded in the eCRF. Any clinically relevant (as determined by the Investigator) deterioration in laboratory assessments or other clinical findings is considered an AE and must be recorded in the subject’s source documents and in the eCRF.

Information about AEs will be collected from Screening (i.e., after the ICF is signed) through 28 days after the last dose of study drug. The AE term should be recorded in standard medical terminology when possible. Also, when possible, signs and symptoms indicating a common underlying pathology should be noted as one comprehensive event. For each AE, the Investigator will evaluate and report the onset date, resolution date, intensity, causality, action taken, serious outcome (if applicable), and whether or not it caused the subject to discontinue the study.

12.2.4. Reporting Serious Adverse Events

All SAEs (related and unrelated) occurring from Screening through 28 days after the last study drug dose are to be reported within 24 hours of first awareness on the part of site staff. Any suspected case of pneumonitis considered an adverse events of special interest, should be reported in the same manner as an SAE.

The Investigator must report all SAEs within 24 hours of discovery via the EDC system, which will trigger email notifications to the Syneos Health, Medical Monitor/Safety team. In the event the EDC system is not available, then SAE reports must be emailed [REDACTED]:

[REDACTED]

Alternatively, a pdf copy of the SAE report form may be faxed [REDACTED]

The Investigator must complete and electronically sign and date the SAE pages of the eCRF and verify the accuracy of the information recorded on the SAE pages with the corresponding source documents.

Additional follow-up information, if required or available, should be submitted within the EDC system within 1 business day of receipt and this should be completed on a follow-up SAE form and placed with the original SAE information and kept with the appropriate section of the eCRF and/or study file.

Sagimet Biosciences is responsible for notifying the relevant regulatory authorities of certain events. It is the Investigator's responsibility to notify the Institutional Review Board (IRB) or Independent Ethics Committee (IEC) of all SAEs that occur at his or her study center.

Investigators will also be notified of all unexpected, serious, drug-related events (i.e., all 7- or 15-Day Safety Reports) that occur during the clinical study. Each study center is responsible for notifying its IRB/IEC of these additional SAEs.

Any incident diagnosis of cancer that occurs in a subject taking part in the study, from the time written informed consent is provided until study completion/exit, must be reported as an SAE ('medically important') within 24 hours of first awareness on the part of site staff.

12.2.5. Follow-Up of Adverse Events

The Investigator must continue to follow all treatment-emergent SAEs and non-serious AEs considered to be at least possibly related to study drug either until resolution or the event is clearly determined to be stable or due to a subject's stable or chronic condition or inter-current illness(es). This follow-up may extend after the end of the study.

12.2.6. Pregnancy

Pregnancies occurring in a female subject while the subject is receiving study drug or within 1 month after the subject's last dose of study drug, or in a female partner of a male subject while the subject is receiving study drug or within 3 months after the subject's last dose of study drug will not be considered serious, but are to be reported using the same procedures as for SAEs described in Section 12.2.1.2.

Study drug is to be held in the event of a positive urine pregnancy test and permanently discontinued for any subject with a positive serum pregnancy test result. The subject should be referred to an obstetrician/gynecologist experienced in reproductive toxicity for further evaluation and counseling.

The Investigator will follow the subject/subject's partner until completion of the pregnancy and must notify the Medical Monitor of the outcome within 5 days. The Investigator will provide this information as a follow-up to the initial report.

If the outcome of the pregnancy meets the criteria for immediate classification as an SAE (i.e., spontaneous abortion [any congenital anomaly detected in an aborted fetus is to be documented], stillbirth, neonatal death, or congenital anomaly), then the Investigator should report it as such. Furthermore, all neonatal deaths that occur within 28 days of birth should be reported, without

regard to causality, as SAEs. In addition, any infant death after 28 days that the Investigator suspects is related to the in utero exposure to the study drug should also be reported.

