8.1. Subject Inclusion Criteria

Subjects meeting all of the following criteria are eligible for enrollment into the study.

1. Must be willing and able to participate in the study and provide written informed consent.
2. Male and female adults ≥ 18 years of age on the date that written informed consent to take part in the study is provided.
3. Body mass index (BMI) $\geq 23 \text{ kg/m}^2$ for Asians and $\geq 25 \text{ kg/m}^2$ for other races.
4. Female subjects must be either:
 - a. Not of childbearing potential (ie, surgically [bilateral oophorectomy, hysterectomy, or tubal ligation] or naturally sterile [>12 consecutive months without menses]).
OR
 - b. Female subjects of childbearing potential must have a negative serum pregnancy (beta-human chorionic gonadotropin [β -HCG]) test during Screening, a negative urine pregnancy test within 24 hours before the first dose of study drug on Day 1, and must agree to perform urine home pregnancy tests monthly between study visits. Female subjects of childbearing potential must not be breastfeeding, not plan to become pregnant during the study, and must use 2 forms of birth control, one being a barrier method (ie, condoms, diaphragm, IUD) throughout the study and for at least 3 months after the final study drug dose. Hormonal contraception (stable ≥ 3 months) and hormonal IUDs are permitted if used with a secondary barrier birth control method (e.g., condoms).
5. Male subjects who have sexual intercourse with a female partner of childbearing potential from the first dose of study drug until 3 months after completion of study drug intake must be either surgically sterile (confirmed by documented azoospermia >90 days after the procedure) OR agree to use a condom with spermicide. All male subjects must agree not to donate sperm from the first dose of study drug until 3 months after completion of study drug intake.
6. Must have liver stiffness measurement $\geq 8.5 \text{ kPa}$ measured by FibroScan and CAP score measured by FibroScan $\geq 280 \text{ dB/m}$ (unless the enrolling study site does not have the capability to measure CAP) during the Screening period.
7. Histologic confirmation of NASH: must have had a prior liver biopsy within 180 days before the Screening visit, or a new biopsy during the screening period, with fibrosis stage F2-F3 and a NAS of ≥ 4 with at least a score of 1 in each of the following NAS components:
 - a. Steatosis (scored 0 to 3)
 - b. Ballooning degeneration (scored 0 to 2)

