10.4. Pregnancy Testing

For female subjects of childbearing potential, a serum beta-human chorionic gonadotropin (β -hCG) pregnancy test will be performed during Screening, and a urine pregnancy test is to be performed within 24 hours before the first dose on Day 1 (Baseline). Subjects with a positive serum pregnancy test result are not eligible for study participation. Serum pregnancy testing is to be repeated at the Week 56 Follow-up visit or at Early Termination (whichever takes place sooner), and during the study any time pregnancy is suspected. Female subjects of childbearing potential are required to perform urine home pregnancy tests monthly between study visits and the results should be recorded in a subject diary. A positive urine test should be followed by an unscheduled serum pregnancy test as soon as possible. Study drug is to be held in the event of a positive urine pregnancy test and permanently discontinued for any subject with a positive serum pregnancy test result. See Section 12.2.6 for details regarding management of any pregnancies during the study.

Female subjects not of childbearing potential must have such documentation included as part of their medical history, ie, surgically [bilateral oophorectomy, hysterectomy, or tubal ligation] or naturally sterile [>12 consecutive months without menses]).

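### Pregnancies in treated women must be reported only to 1 month after the last dose, although the protocol requires their contraception, and reporting for male subjects' partners, for 3 months

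*Protocol*

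**What the plan says.** Section 12.2.6 of the protocol sets two reporting windows in one sentence. The first covers a pregnancy in a female subject "while the subject is receiving study drug or within 1 month after the" last dose. The second covers a pregnancy "in a female partner of a male subject while the subject is receiving study drug or within 3 months after the" last dose.

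The contraception rules are elsewhere. Section 8.1 criterion 4b requires women of childbearing potential to use two methods "throughout the study and for at least 3 months after the final study drug dose". The Synopsis and Section 5.2 repeat this. For men, criterion 5 sets the contraception period as "from the first dose of study drug until 3 months after completion of study drug intake".

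General safety collection is shorter. Section 12.2.1.1 collects adverse events "through 28 days after the last dose of study drug, whether or not they are related to the study drug", and Section 12.2.4 covers serious adverse events "occurring from Screening through 28 days after the last study drug dose are to be reported within 24 hours". Section 10.4 places the last scheduled serum pregnancy test at the Week 56 Follow-up visit or at Early Termination, whichever is sooner. The SAP (5.2 Safety) lists pregnancy test results as a safety endpoint but sets no reporting window.

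**The concern.** For men, the period of required contraception and the period in which a partner's pregnancy must be reported are both 3 months. For women, who take the drug themselves, contraception is required for 3 months but reporting stops at 1 month.

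If a treated woman conceives in the second or third month after her last dose, the protocol does not oblige the site to report the pregnancy or follow it to outcome. If a male subject's partner conceives in the same months, both are obligatory. What is at stake is the completeness of pregnancy outcome data for a drug with a stated contraception requirement. Efficacy is not touched.

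**Working it through.** The plan gives no figure to reproduce here, so the check compares the stated periods and then sizes the gap.

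**Periods after the last dose**

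| Item | Protocol section | Length |
|---|---|---|
| Contraception, women | 8.1 criterion 4b; Synopsis; 5.2 | at least 3 months |
| Pregnancy reporting, women | 12.2.6 | 1 month |
| Contraception, men | 8.1 criterion 5 | 3 months |
| Pregnancy reporting, men's partners | 12.2.6 | 3 months |
| AE and SAE collection | 12.2.1.1, 12.2.4 | 28 days |
| Last scheduled serum pregnancy test | 10.4 | Week 56, about 4 weeks, or Early Termination if sooner |

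**Does another section close the gap?** No.
- Complications and terminations of pregnancy count as adverse events under 12.2.1.1, but only within the 28-day window.
- Section 12.2.5 extends follow-up of events already captured. It does not open a new reporting period.
- When dosing is extended (7.1), the Follow-up visit moves to four weeks after the last dose, so the interval after dosing is no longer.
- The 12.2.6 rule to follow a pregnancy to completion applies to pregnancies that were reportable in the first place.
- One clause in 12.2.6 has no limit tied to the last dose: an infant death after 28 days that the investigator suspects is due to exposure in utero. It catches a single rare outcome and depends on the site knowing of the pregnancy.

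**Length of the gap**
- Contraception required but reporting not: 3 − 1 = 2 months = 365.25 × 2/12 = 60.9 days.
- No scheduled contact: 3 months is 13.0 weeks and Week 56 − Week 52 = 4 weeks, so 13 − 4 = 9 weeks.

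**Expected pregnancies in the gap.** The documents give neither the number of women of childbearing potential nor a pregnancy rate. Both ranges below are assumptions: 10–30% of subjects, and 1–5 pregnancies per 100 woman-years on two methods.
- TVB-2640 arm, low: 108 × 10% = 10.8 women; × 2/12 year = 1.8 woman-years; × 0.01 = 0.018.
- TVB-2640 arm, high: 108 × 30% = 32.4 women; × 2/12 year = 5.4 woman-years; × 0.05 = 0.27.
- Both arms, since sites are blinded and 12.2.6 applies to everyone, low: 162 × 10% × 2/12 × 0.01 = 0.027.
- Both arms, high: 162 × 30% × 2/12 × 0.05 = 0.405.

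So 0.02–0.27 pregnancies would be expected on active drug, and 0.03–0.41 reports across the trial.

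**The case against.** The strongest reply is that no instruction contradicts another. The contraception rule tells the subject what to do, the reporting rule tells the site what to report, and a site can comply with both. Nothing in the documents says the two periods must be equal, and a contraception period may carry a safety margin beyond the time of exposure. The sentence in Section 5.2 that leads to the contraception rule is redacted and no half-life is visible, so the documents cannot show that a conception in the second or third month is drug-exposed. The 1-month limit also fits the 28-day adverse event window and the follow-up test at about 4 weeks.

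Much of this stands. This is a design choice rather than a contradiction, exposure in those months cannot be shown, and the fit with the 28-day schedule is a plausible origin for the limit. Because of the redaction, the absence of a visible reason is not evidence that none exists.

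It does not dispose of the point. The partner limit, in the same sentence, already goes beyond 28 days, so the protocol accepts pregnancy reporting outside the general safety window. One could add that exposure through a male subject is a different route, so the partner window is no benchmark for women. But partner reporting matches the men's own contraception period, so the protocol aligns the two for men and not for women. The mismatch between women's contraception and women's reporting remains even if the comparison with men is set aside.

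It is also fair to say that the gain is small: voluntary reports are not barred, and ascertainment after the last visit would be passive.

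**Conclusion.** The concern holds, as a minor point. Mandatory pregnancy reporting for female subjects ends about 61 days before their required contraception does, and no other provision in the protocol or SAP covers the interval. On the assumed ranges the expected number of affected pregnancies is 0.02–0.27 on TVB-2640 (0.03–0.41 over both arms), so most likely none would occur. The length of the gap rests on the protocol's text alone; the count rests on assumptions about the share of women of childbearing potential and the contraceptive failure rate. No claim is made that a conception in the gap would be drug-exposed, and no efficacy result depends on it.

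**What to change.** In 12.2.6, replace the 1-month limit for female subjects with 3 months, so that it matches 8.1 criterion 4b and the partner limit in the same sentence. At the Follow-up or Early Termination visit, instruct women of childbearing potential to tell the site if they become pregnant within 3 months of the last dose.

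The cost is one changed phrase, one instruction at an existing visit, and probably no more than one extra report with outcome follow-up. Ascertainment after the last visit would be passive, as it already is for male subjects' partners. Active ascertainment would need one telephone contact per woman of childbearing potential at about 3 months, which the expected count does not justify. If dosing has already finished, the correction belongs in any later protocol that reuses this section.
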